7.6 Additional Information on Performance Analyses

7.6.1 Subgroup Performance Analyses

Response in participants will be analysed overall and for the following subgroups:

- Biological sex (male or female)
- Age group (5-year age groups: 45-49, 50-54, 55-59, and 60-64)
- Ethnicity (White / Mixed / Asian or Asian British / Black African, Caribbean or Black British / Other)
- Education level (Early Education / Further Education / Higher Education)

Response in HCP individuals will be analysed overall and for the following subgroups:

- Practice role (GP / nurse / other)
- Study role (making decisions on care plans / not making decisions on care plans)
- By study site

Additional subgroup analyses may be performed if deemed necessary.

7.6.2 Further Exploratory Performance Analyses

Further exploratory analyses of Performance may be performed at the Sponsor's discretion.

All exploratory analyses will be described as such in the CSR.

7.7 Safety Analyses

Safety assessments include treatment emergent adverse events and device deficiencies as per protocol.

All safety analyses will be performed by cohort and overall based on the Enrolled Participant Analysis Set.

7.8 Interim Analysis

An interim performance analysis will be performed when approximately half of the participants have been recruited, and approximately 100 V3PartQ questionnaires have been completed. Importantly, the interim analysis will not be used to deviate from the study protocol, nor will the results be used to compete with or contradict the final analysis. Once performed, the final analysis will be the source of truth for all questions relating to the study objectives.

The interim analysis will serve two purposes:

- To check for demographic balance across sex, age and ethnicity groups. If imbalances are found, steps will be taken to redress the imbalance, in order to adhere to Protocol specifications.

- To check the integrity of the HEART study reporting mechanisms. For this purpose, all endpoints described in the table in Section 7.5 will be analysed to check that reports are correctly generated.

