#### **7.1.8. Visit 2, Receiving CVD IRT results and study participant management**

Approximately 5-12 weeks after the blood sample collection, the CVD IRT result will be available. The study staff will be notified of its availability by email and will be able to download the CVD IRT report from The HEART Application. Study personnel will be trained on the content of the report and best practice on sharing genetic information. Only those trained and listed on the delegation log will be permitted to share the CVD IRT results with the participants.

Current NICE guidance recommends intervention if the ten-year risk of CVD is greater than 10%. Both QRISK®2 and CVD IRT produce estimates of 10-year CVD risk, therefore, where the QRISK®2 and / or the IRT score exceeds 10%, NICE guidance is recommended to be followed.

The IRT report will be available up to 12 weeks after the sample is taken. If QRISK®2 indicates intervention is needed within this timeframe, the physician's discretion should be used.

The HCP will determine the best method of sharing the results (QRISK®2 and CVD IRT) as per standard practice. Participants may be contacted by phone or videoconference or may be asked to attend the clinic in person.

At Visit 2 the following data will be collected:

- date of visit
- the method of sharing results, e.g., phone, videoconference or clinic visit
- who shared results, e.g., GP or nurse
- whether QRISK®2 score required change in treatment (e.g., statin, life style, both or none influenced the change)
- any change in treatment (e.g. statin)

- if the participant's CVD IRT score was higher than their QRISK score, whether the CVD IRT score influenced (or informed on) a change in treatment (e.g. statin, lifestyle, both or none)
- what treatment was changed
- the participant will be asked about any potential adverse events since the previous visit.

The report is intended for HCP use to share results, but if requested by the participant a copy can be provided. The participant should be reminded of the online questionnaire and its importance to the study which will be sent to their email address in around 0-14 days' time. The study staff should also ensure that the participant's personal email address is available and correct on the enrolment log, for the above purposes and for participation in Interviews, if required by NECS.

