### 7.6.1. Questionnaires

Visit 1 (baseline): Participants will be asked to complete a paper questionnaire consisting of four questions. Participants will complete after the study procedures have been completed and just prior to leaving the GP Surgery. The study staff will enter the data into the eCRF and keep the questionnaires filed in the site file as source data.

Visit 2: HCPs will be asked to complete a focused questionnaire via the eDC.

Visit 3: An online questionnaire (using SurveyMonkey) will be sent to study participants and HCPs to complete. The questionnaires, different for participants and HCPs, are mixed qualitative and quantitative questionnaires designed to capture their understanding and perception of the CVD IRT as well as its usefulness and impact.

All participants who completed Visit 2 will be requested to complete an online mixed quantitative and qualitative questionnaire. A link will be emailed by the site staff to the patients' personal email address up to 14 days after the receiving test results, and patients will be reminded once to complete the questionnaire. If there is no response after 4 weeks, the questionnaire will be closed to the participant. The target minimum response rate is 20%.

All HCPs involved in the study will be emailed a link to the HCPs' work email address after at least  $\frac{2}{3}$  of that site's participants or at least  $\frac{2}{3}$  of the total study participants (whichever is first for each site) have completed visit 2. HCPs will be reminded to complete the questionnaire no more than twice. HCPs are expected to respond to the questionnaire within three weeks of issue. The target response rate is 50%.

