### **10.2. Planned recruitment rate**

It is planned that each of the 10 to 12 sites recruit between 5 and 10 participants per week. Based on this, and allowing for staggered site initiations, it is anticipated that recruitment will take between 5 and 7 months.

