3.3 Study Duration

The recruitment period will be 30 weeks. The duration of participant involvement will be between approximately 14 and 20 weeks, from consent to completion to the final interview (if selected).

It is expected that the study will take approx 10 months to complete.

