3.4 Sample Size

The aim of this study is to demonstrate that predictive genetic testing can be incorporated into primary health care. This study is adding genetic testing to a tool that is already available; QRISK®2 predicts the likelihood of developing CVD over the next 10 years by assessing clinical data. It is intended that the addition of a genetic component to the test should not complicate the process, maintaining ease of use.

To this end it is planned to select sites of different size, capacity and resource to test assimilation of the genetic component into their varying processes. Additionally, the addition of the genetic component should not hinder the number of assessments normally undertaken, therefore high throughput is essential.

Also of interest to the study is a diverse population. The study will aim to recruit an equal number of male and female, even numbers across the 5 year age brackets (e.g., 45-49 years), and also aim to include 10-15% black, asian and minority ethnic (BAME) participants.

It is considered that 8-10 sites from areas of varying affluence and deprivation, and recruiting a high number of participants reflective of normal practice (around 100) will serve to answer the study objectives. It is planned to recruit around 1000 participants from 8-10 sites. All participants will be invited to complete an online survey. Of the participants who complete the survey a subset of 20-30 participants will be invited to take part in a telephone interview.

Approximately 30 HCPs involved in delivering the study will be invited to complete a questionnaire and take part in a focus group.

Approximately 5 representatives of the PCCs will be invited to take part in a focus group.

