7.9 Timing of Analyses

The final analysis of the study will be performed after all participants have completed their final visit and the subgroup have completed interviews or have withdrawn before then.

The interim analysis will be carried out once approximately half of the participants have been enrolled.

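### SAP 7.8 and 7.9 give different interim triggers; at the 20% minimum questionnaire response, the one in 7.8 would fall at about 67% to 97% enrolled or later, which can leave little room for the demographic rebalancing

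*SAP*

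**What the plan says.** SAP 7.8 places the interim at the point when "approximately half of the participants have been recruited, and approximately 100 V3PartQ questionnaires have been completed". SAP 7.9 gives one condition: "The interim analysis will be carried out once approximately half of the participants have been enrolled". Neither section says which governs.

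SAP 7.8 gives the interim two purposes. The first is to check balance across sex, age and ethnicity: "If imbalances are found, steps will be taken to redress the imbalance, in order to adhere to Protocol specifications". The second is to check that the study's reports are generated correctly. The balance aims are in Protocol 10.1 and SAP 3.4: equal numbers of men and women, even numbers across the 5-year age bands, and 10-15% BAME participants.

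On timing, Protocol 7.1.8 states: "Approximately 5-12 weeks after the blood sample collection, the CVD IRT result will be available". The V3PartQ link follows within 14 days of results, and participants have at least 4 weeks to complete it (Protocol 7.1.9 and 7.6.1). On response, Protocol 7.6.1 states: "The target minimum response rate is 20" per cent. On accrual, SAP 3.3 states: "The recruitment period will be 30 weeks". Protocol 10.2 is looser: "it is anticipated that recruitment will take between 5 and 7 months".

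**The concern.** One analysis has two stated triggers, and the extra condition in SAP 7.8 counts forms that arrive weeks after the participants who complete them enrol. If response is near the stated minimum, the interim waits well beyond half enrolment.

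The second purpose can tolerate that wait; the first cannot. Steering recruitment works only while enough participants remain to be recruited. Age, sex and self-identified ethnicity are all collected at Visit 1 (Protocol 7.1.7.1), so the balance check would be waiting for data it does not use. What is at stake is whether a planned safeguard for the recruitment aims runs while it can still work.

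**Working it through.** **Inputs.** N = 1000 (SAP 3.4). Recruitment T = 30 weeks (SAP 3.3). Response r = 20% as a minimum (Protocol 7.6.1). Lag L from enrolment to completed form: 5-12 weeks to Visit 2, plus 0-2 weeks to the link, plus 0-4 weeks to complete. That is 5 to 14 weeks up to the link and 18 weeks at most. Assumptions not in the documents: even accrual (1000/30 = 33.3 per week), no loss before Visit 3, and one common lag for everyone.

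**1. The plan's own pairing.** 100 forms from 500 participants is 100/500 = 20%. The two conditions in SAP 7.8 therefore match exactly at the minimum response, but only if the lag is ignored.

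**2. Timing at 20% response.** Week of the 100th form = (100/r)/33.3 + L = 15 + L. Forms available at half enrolment (week 15) = r × 33.3 × (15 − L).

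| Lag (weeks) | Week of 100th form | Enrolled by then | Forms at week 15 |
|---|---|---|---|
| 5 | 20 | 667 (67%) | 67 |
| 8 | 23 | 767 (77%) | 47 |
| 11 | 26 | 867 (87%) | 27 |
| 14 | 29 | 967 (97%) | 7 |
| 18 | 33 | recruitment closed | 0 |

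**3. Sensitivity to response.** Percentage enrolled when both conditions are met; 50% means that half recruitment is the later condition. The 11.5-week column takes the middle of each window (8.5 + 1 + 2).

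| Response | Lag 5 | Lag 8 | Lag 11.5 | Lag 14 |
|---|---|---|---|---|
| 20% | 67% | 77% | 88% | 97% |
| 30% | 50% | 60% | 72% | 80% |
| 40% | 50% | 52% | 63% | 72% |
| 50% | 50% | 50% | 58% | 67% |

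Example: at 40% and 8 weeks, 250/33.3 + 8 = 15.5 weeks, and 15.5/30 = 52%.

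**4. Sensitivity to accrual, at 20% response.** Over 5 months (21.7 weeks), the 500th participant enrols at week 10.85. A 5-week lag gives 15.85/21.7 = 73%, and a 12-week lag gives week 22.85, after recruitment has closed. Staggered site starts also push the trigger later. With a linear 10-week ramp within 30 weeks, the full rate is 1000/25 = 40 per week and 200 are enrolled by week 10. The 500th enrols at week 17.5, and a 5-week lag gives week 22.5 with 200 + 12.5 × 40 = 700 (70%) enrolled.

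**5. Room to rebalance.** The starting imbalances are illustrative; the documents give none. With n enrolled at the check:

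- BAME share needed afterwards to move from 5% to 10% overall = (100 − 0.05n)/(1000 − n).
- Share of the over-represented sex needed afterwards to move from 60/40 to 50/50 = (500 − 0.6n)/(1000 − n).

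| Enrolled at check | BAME share needed | Sex split needed |
|---|---|---|
| 500 | 15% | 40/60 |
| 667 | 20% | 30/70 |
| 750 | 25% | 20/80 |
| 867 | 43% | not possible |
| 967 | not possible | not possible |

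A 60/40 split passes the point of correction when 0.6n = 500, which is n = 833. Around 85% enrolled is therefore a fair mark for little or no room.

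**The case against.** A reader might infer that SAP 7.8 and 7.9 contradict each other. They do not, strictly. Section 7.9 leaves out the questionnaire condition without excluding it, and an interim meeting both conditions in 7.8 also comes once half are enrolled. What stands is that the wording differs and gives different dates.

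The timing result leans on 20%, which is a floor and not a forecast. The documents give no expected response. At 40-50% with an 8-week lag the conditions roughly coincide, so it would be wrong to say that they never can. Even so, with mid-window lags the trigger still falls at 58-72% enrolled for 30-50% response.

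The longest lags stack the slowest result, the latest link and last-day completion for everyone, so the upper end is a bound and not a typical case.

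The interim is also not the only possible control. Sites are to be chosen for diversity (Protocol 4 and 10.1), a Study Management Group meets regularly to review progress, and the demographic targets are aims. All of that is fair, but no other step is assigned the balance check; SAP 7.8 assigns it to the interim.

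**Conclusion.** The two sections state different triggers and must be reconciled. Under even accrual of 1000 over 30 weeks and response at the 20% minimum, the joint trigger would be met at about 67% enrolled (5-week lag) to 97% (14-week lag), or after recruitment closes (18-week lag). Faster or staggered accrual moves it later; higher response moves it earlier.

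The tempting stronger reading is that the check always comes too late. The figures do not support that. At 67% enrolled, a third of recruitment remains and moderate imbalances can be corrected, with more effort than at half enrolment. The loss becomes serious from about 85%.

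Nor does the mistiming threaten inference. The plan specifies no hypothesis test at the interim, and SAP 7.8 makes the final analysis authoritative. The consequence is confined to steering recruitment.

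Confidence is high on the wording mismatch. The size of the delay depends on the response, lag and accrual assumptions above.

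**What to change.** Split the interim in SAP 7.8:

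- Run the demographic balance check on Visit 1 data when about 500 participants are enrolled, whatever the number of V3PartQ returned.
- Run the reporting-mechanism check when about 100 V3PartQ are available.

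Reword SAP 7.9 to state the same two time points. The cost is SAP wording and one additional demographic table. There is no error-rate consequence, and no new data collection is needed.

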7.9 Timing of Analyses

The final analysis of the study will be performed after all participants have completed their final visit and the subgroup have completed interviews or have withdrawn before then.

The interim analysis will be carried out once approximately half of the participants have been enrolled.

7.10 Data Review Meeting

A data review meeting will be convened by the Sponsor at the following timepoints

- Before any administrative analyses
- Before the final analysis
- Before the follow-up analyses.

Each data review meeting will take place after the data have been cleaned but prior to the database being locked for analysis.

The terms of reference of the Data Review Meeting before the final analysis shall include but not be limited to:

- The determination of whether protocol deviations / violations are 'major' or 'minor', or not a protocol violation at all
- The allocation of subjects to analysis sets
- A review of missing data and of outliers
- A decision on whether centres need to be combined
- A review of the distribution of the Performance variables, considering any implications for the proposed method of statistical analysis
- A review of whether additional covariates need to be included in the analyses
- The finalisation of the SAP

The Data Review Report will be an Appendix to the CSR.

7.11 Changes from Analyses Specified in the Protocol

No changes have been issued or planned.
